# 9.2.3 Exploratory Outcome Measures

- 9.2.3.1 Change from baseline to week 26 in HOMA-IR.
- 9.2.3.2 Change from baseline to week 26 in LDL, HDL, non-HDL cholesterol, and triglycerides.
- 9.2.3.3 Change from week 26 to week 38 in systemic inflammation markers (IL-6, IP10, sCD163, sTNF-RI, oxidized LDL, and KT ratio).
- 9.2.3.4 Gastrointestinal microbial diversity from fecal samples at entry and postentry visits.
- 9.2.3.5 Change in gastrointestinal symptoms from baseline to 26 weeks.

9.2.3.6 Assess diversity of gut microbiome based on dietary recall.

#### 9.3 Randomization and Stratification

After eligibility is confirmed, participants will be randomized at a 1:1 ratio (Visbiome Extra Strength: placebo) using permuted blocks without institutional balancing with stratification by intent and eligibility to enroll in the substudy A5352s. Because the stratification is to ensure balance between the treatment arms within A5352s and is not felt to affect A5350 outcomes, the stratification will not be taken into account in analyses.

# 9.4 Sample Size and Accrual

The primary objective of this study is to compare sCD14 change over 24 weeks of treatment in participants randomized to Visbiome Extra Strength compared to placebo. The sample size calculations are based on the primary hypothesis testing  $H_0$ :  $\mu_{Visbiome\ Extra}$  strength =  $\mu_{placebo}$  targeting 90% power in the comparison of changes in  $log_{10}$ -transformed sCD14 between Visbiome Extra Strength and placebo.

Our estimate of the standard deviation for the change in plasma sCD14 levels over 24 weeks of treatment comes from a recent placebo-controlled trial of maraviroc intensification among ART-suppressed, HIV-infected individuals [98]. Among the 20 placebo-treated participants, the mean change in plasma sCD14 levels from baseline to week 16 was +0.003 log10 ug/ml (SD: 0.11) when analyzing a single measurement at each time point and -0.005 log10 ug/ml (SD: 0.06) when taking the average of two measures at each time point. Although we plan to take the average of two sCD14 levels at both baseline and week 26, we have conservatively powered the study assuming the SD is 0.09 log10 ug/ml.

A 0.07 log10 sCD14 between-arm difference was associated with a 23% decreased odds of a non-AIDS event or non-accidental death at the pre-event time point [56] and is considered as clinically significant, and therefore was chosen as the effect size for this study.

A total sample of 90 participants (45 per arm) is needed to detect a difference of 0.07  $log_{10}$  in sCD14 levels between Visbiome Extra Strength and placebo with 90% power and a 0.05 two-sided type I error rate, under the assumption that the SD of the changes in  $log_{10}$  sCD14 from baseline to week 26 is 0.09 for both arms.

Although it is expected that Visbiome Extra Strength will be well tolerated in this study, it is anticipated that there will be some missing data due to laboratory complications and loss to follow-up. The sample size is inflated by 20% to account for missing data.

The following table summarizes the calculation of the sample sizes corresponding to the detection of various effect sizes under various assumed standard deviations, with the effect size, standard deviation, and adjusted sample size selected for this study shown in bold.

Effect size in log 10 sCD14 (difference between Visbiome Extra Strength and placebo)	Std Dev of ∆ Baseline to Week 26	Total Sample size (90% power, alpha=0.05)	Adjusted Sample Size (20% inflation)
0.03	0.05	60*2=120	75*2=150
	0.07	116*2=232	145*2=290
	0.09	191*2=382	239*2=478
0.05	0.05	23*2=46	29*2=58
	0.07	43*2=86	54*2=108
	0.09	70*2=140	88*2=176
0.07	0.05	12*2=24	15*2=30
	0.07	23*2=46	29*2=58
	0.09	36*2=72	45*2=90

For each continuous secondary endpoint, change from baseline to week 26 will be compared between treatment arms. The following table summarizes the power to detect various effect sizes as well as the precision of the effect size estimate.

Comparison of 2 arms (36 vs. 36 evaluable participants)				
Effect Power Width of 95% Size CI				
0.77*SD	90%	± 0.47*SD		
0.67*SD	80%	± 0.47*SD		
0.59*SD	70%	± 0.47*SD		

#### Accrual

We expect to enroll an average of two study participants per month at each site and expect to complete enrollment within 9 months (2 participants x 5 sites over 9 months = 90 participants) once all sites are registered. Should more sites register for the trial, enrollment will occur more rapidly.

# 9.5 Monitoring

Accrual, a summary of AEs, and sample/data availability will be reviewed monthly by the protocol core team. This summary will be pooled over the study arms. In addition, baseline characteristics as well as early study product and study discontinuations (and reasons) will be reviewed regularly by the protocol core team. The Statistical and Data Analysis Center (SDAC) will also provide a report of all reported AEs by blinded treatment arm, to be reviewed quarterly by the DAIDS clinical representative or designee.

An ACTG-appointed Study Monitoring Committee (SMC) will review accrual, adverse event summaries, off-product and off-study rates and reasons, and sample/data availability, broken down by study arm. The first SMC review will occur 6 months after

the first participant is enrolled and then every 6 months as long as participants remain in follow-up. In addition, longitudinal changes in CD4+ T-cell count and HIV-1 RNA levels will be reviewed. Note that biomarker measurements will be run in batches after follow-up is concluded, and, therefore these data are not expected to be available at interim reviews. The SMC may also be convened if a reason is identified by the DAIDS clinical representative, study chairs, or study statistician in consultation with the team.

# 9.6 Analyses

All statistical tests will be two-sided with a nominal alpha level of 0.05. Because this is a phase II study and all potential biologic activities of the intervention are of interest, analyses will be as-treated, and limited to participants who 1) have baseline and week 26 sCD14 measurements, 2) remain on study product through week 26 (participants with more than 50% on average of missed study product may be excluded), 3) have not used prohibited medications, 4) do not have a confirmed virologic failure (as defined per section 6.2.3 at or prior to week 26, and 5) do not experience inflammatory conditions, receive vaccines, or have concurrent illness (as defined per section 6.2.3).

NOTE: Participants experiencing inflammatory conditions at the time of a visit are instructed to wait 7 days before measurements are obtained. Measurements obtained while inflammatory conditions are present will not be included in the analysis. A supplemental intent-to-treat analysis will also be performed and will include all randomized participants. No adjustment for multiple testing will be performed. A summary of the number of participants experiencing study product-related AEs and the types of AEs will be reported, as will the proportion of participants who discontinue study product after entry.

To reduce intra-participant variability, two blood draws will be performed at baseline (entry and week 2) and week 26 (week 25 and week 26) and the measurements will be the average of two for sCD14. If repeat measurements are not available at either of these time points, a single measurement will be used rather than the average.

#### 9.6.1 Primary Analysis

The primary objective of the study is to assess the effect of Visbiome Extra Strength on sCD14 in HIV-infected participants well-controlled on ART. To address this, changes in sCD14 from baseline to week 26 will be compared between the Visbiome Extra Strength arm and the placebo arm by linear regression. For this model each participant will have a single outcome measure of sCD14 change from baseline to week 26. The only predictor variable will be study arm.

Two supplemental linear regression analyses will be performed. The first will additionally adjust for baseline sCD14 values (continuous) while the second will assess differential Visbiome Extra Strength effects by baseline sCD14 tertile by additionally adjusting for the sCD14 tertile main effect and the study arm by sCD14 tertile interaction.

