#### 9.2 Outcome Measures

#### 9.2.1 Primary Outcome Measure

Change in sCD14 from baseline to week 26.

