4.1 Analysis Populations

Intent-To-Treat (ITT): All randomized participants.

Modified Intent-To-Treat (mITT): All randomized participants who started study product.

Per-Protocol (PP): All eligible, randomized participants who 1) have baseline and week 25/26 sCD14 measurements, 2) remain on study product through week 26 (participants with more than 50% on average of missed study product may be excluded), 3) have not used prohibited medications, 4) do not have a confirmed virologic failure (as defined per section 6.2.3 at or prior to week 26, and 5) do not experience inflammatory conditions, receive vaccines, or have concurrent illness (as defined per section 6.2.3).

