4.4 Statistical Summaries and Testing

All statistical tests will be two-sided with a nominal alpha level of 0.05 and no adjustment for multiple testing.

Specimens collected 1 day after the last dose of study treatment will be considered "on treatment".

Specimens collected within 6 days of an influenza vaccination will not be used for analysis unless the vaccination and specimen collection occurred on the same date and the site has documented that the vaccination was given after specimen collection.

Outcome measures will be transformed for analyses and summaries on the log₁₀ scale, as appropriate, if determined to not be approximately normally distributed.

Because the stratification is to ensure balance between the treatment arms within A5352s and is not felt to affect A5350 outcomes, the stratification will not be taken into account in analyses.

Safety analyses will summarize the highest grade AE by participant using the mITT population and will compare treatment arms using the Wilcoxon rank-sum test. All AEs and AEs related to study treatment will be analyzed.

For all continuous outcome measures, tabular and graphical data summaries will be provided for both cross-sectional values across study weeks and change from baseline to post-baseline study weeks and will use the PP population. Mean changes in outcome measures will be compared between arms with either a two-sample t-test with equal variances or an adjusted linear regression model, as appropriate. The mean difference and 95% confidence interval (CI) will be provided along with the associated p-value.

For the primary analysis, two supplemental linear regression analyses will be performed. The first will additionally adjust for baseline sCD14 values (continuous) while the second will assess differential Visbiome Extra Strength

effects by baseline sCD14 tertile by additionally adjusting for the sCD14 tertile main effect and the study arm by sCD14 tertile interaction.

Correlations will be assessed with scatter plots as well as the Spearman correlation coefficient and associated p-value using the PP population.

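### The primary sCD14 model omits the baseline covariate that every analysed participant has, and the SAP does not fix the log10 scale on which the trial was powered

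*Protocol*

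**What the plan says.** **Model.** The primary outcome in Protocol 9.2.1 is "Change in sCD14 from baseline to week 26", with no scale given. Protocol 9.6.1 compares that change between arms by linear regression and specifies: "The only predictor variable will be study arm". Baseline sCD14 as a continuous covariate appears only in the first of two supplemental regressions, and SAP 4.4 keeps it supplemental. The primary population in Protocol 9.6 is limited to participants who "have baseline and week 26 sCD14 measurements". The per-protocol definition in SAP 4.1 likewise requires that they "have baseline and week 25/26 sCD14 measurements". For continuous outcomes in general, SAP 4.4 compares mean changes with "either a two-sample t-test with equal variances or an adjusted linear regression model, as appropriate".

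**Scale.** Protocol 9.4 sizes the trial for changes in log10-"transformed sCD14 between Visbiome Extra Strength and placebo", with a difference of 0.07 and an SD of 0.09, both in log10 units. The only transformation rule in the SAP is in section 4.4: outcomes go to log10 "as appropriate, if determined to not be approximately normally distributed". It sets no criterion, does not say whether levels or changes are to be checked, and does not treat sCD14 separately.

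**The concern.** Subtracting baseline is not the same as adjusting for it. A change score fixes the baseline coefficient at 1, and regression estimates it. When baseline and follow-up are imperfectly correlated, the estimated coefficient leaves less residual variance. No one is lost by adjusting, because baseline sCD14 is already a condition of entering the analysis. The primary set is also restricted by events after randomisation (adherence, prohibited medication, virologic failure, intercurrent illness), so balance on baseline sCD14 is not assured there.

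On scale, a literal reading of SAP 4.4 lets the observed distribution decide the units of the primary test and of its estimate. The 0.07 target and the SD of 0.09 have meaning only in log10. There, 0.07 corresponds to a ratio of 10^-0.07 = 0.851, a level about 15% lower. A mean difference in raw concentration units cannot be compared with that target. On skewed data the raw-unit test would also have somewhat less power than planned.

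**Working it through.** **Inputs from the documents.** Difference 0.07 log10, SD of change 0.09, two-sided alpha 0.05, 36 evaluable and 45 randomised per arm (Protocol 9.4). Protocol 9.4 also reports an SD of 0.06 when two draws are averaged at each time point, and Protocol 9.6 plans that averaging.

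**Assumptions.** The correlation rho between baseline and week 26 log10 sCD14 is not given. I take 0.5, 0.7, 0.8 and 0.9, with equal variance at the two times.

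**1. The plan's own figure.** Noncentrality = 0.07 / (0.09 × sqrt(2/36)) = 0.07 / 0.02121 = 3.30 on 70 df, giving power 90.2%. Then 36 / 0.8 = 45 per arm. The stated sample size is reproduced for the arm-only test on log10. The 95% CI half-width is 1.994 × 0.02121 = 0.0423. At SD 0.06 power is 99.8%.

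**2. Adding baseline.** With variance s² at each time, the change has variance 2s²(1 − rho). After regression on baseline the residual variance is s²(1 − rho²). The ratio is (1 + rho)/2, so residual SD = 0.09 × sqrt((1 + rho)/2). The arm contrast has variance factor (2/36)(1 + F/70). Here F follows F(1,70) and allows for chance baseline imbalance; power is averaged over it, with 69 df.

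| rho | residual SD | power | CI half-width | power at SD 0.06 |
|---|---|---|---|---|
| arm only | 0.0900 | 90.2% | 0.0423 | 99.8% |
| 0.5 | 0.0779 | 96.2% | 0.0369 | 99.99% |
| 0.7 | 0.0830 | 93.9% | 0.0393 | 99.95% |
| 0.8 | 0.0854 | 92.6% | 0.0404 | 99.92% |
| 0.9 | 0.0877 | 91.2% | 0.0415 | 99.87% |

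Without the imbalance term the powers at SD 0.09 are slightly higher: 96.4%, 94.2%, 92.9% and 91.6%.

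**3. Scale.** I simulated 4,000 trials per setting with bivariate normal log10 values, SD of change 0.09, baseline SD = 0.09 / sqrt(2(1 − rho)), effect −0.07 and an equal-variance t-test. The SAP gives no criterion, so I assumed that raw units are kept when Shapiro-Wilk p > 0.05, checked either on change or on baseline. "Differs" below is the share of trials whose significance verdict is not the log10 verdict. Monte Carlo SE is about 0.5 points on power.

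| rho | log10 power | change checked: raw kept / power / differs | baseline checked: raw kept / power / differs | always raw: power / differs |
|---|---|---|---|---|
| 0.5 | 90.0% | 89% / 86.9% / 3.8% | 56% / 88.5% / 2.2% | 86.6% / 4.4% |
| 0.7 | 90.3% | 82% / 86.7% / 4.5% | 35% / 88.7% / 1.9% | 85.6% / 5.9% |
| 0.8 | 90.7% | 72% / 86.1% / 5.4% | 19% / 89.8% / 1.0% | 83.9% / 7.9% |
| 0.9 | 90.8% | 41% / 87.4% / 4.1% | 3% / 90.6% / 0.3% | 80.9% / 11.4% |

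The always-raw column depends on the spread of levels. At an assumed cross-sectional log10 SD of 0.30 (rho about 0.955) it falls to 69%. At SD of change 0.06, the rule gives power of at least 99.5% and the verdict differs in at most 0.3% of trials. With no true effect and SD 0.09, rejection under the rule is 4.7% to 5.5%.

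**The case against.** The arm-only test is valid under randomisation and correctly sized, and the adjusted model is already prespecified, so only the label of primary would move. The gain depends on a correlation that no document supplies. At a correlation of 0.9 it is one point, and if the averaged-draw SD of 0.06 holds there is nothing to gain. All of this stands, and it is why the point is put as precision only.

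In a per-protocol set the two models could also differ in expectation, not just in precision, if the arms differ at baseline. That is fair. It is a reason to keep the arm-only model as a sensitivity analysis, not a reason to leave baseline out of the primary one.

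On scale, Protocol 9.4 ties the primary hypothesis to log10, and the SAP sentence is a general rule for all outcomes that never claims to override it. A raw-unit test follows only if that sentence is read alone. The reading is reasonable, but SAP sections 3.1 and 4.4 nowhere say so for sCD14. The sizes in the simulation do rest on an assumed normality criterion, log-normality and an assumed correlation.

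The open choice of test in SAP 4.4 is also nearly closed for sCD14. An equal-variance t-test is the same test as regression on arm alone, and the SAP then labels the adjusted model supplemental.

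**Conclusion.** Both points hold, and both are modest. Neither is an error in the sample size or a bias in the planned test.

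- **Covariate.** Adjustment adds 1.0 to 6.0 points of power at SD 0.09 and narrows the confidence interval by about 2% to 13% (0.0423 to 0.0415, and to 0.0369). The smaller gains go with the higher correlations. The sizes rest on the assumed range of rho and on equal variances at the two times.
- **Scale.** This is a gap between the Protocol and the SAP on the primary endpoint. Its main cost is an estimate that might not be readable against the 0.07 log10 target. Under the assumed rule the loss of power is at most about 5 points (90.7% to 86.1%), and the verdict changes in 0.3% to 5.4% of trials at SD 0.09. Larger losses need raw units to be used always. There is no material type I error concern.

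The two effects should not be added at their extremes: adjustment helps most at low correlation, and always using raw units costs most at high correlation. The change is worth making because it is free.

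**What to change.** In Protocol 9.6.1 and SAP 4.4, define the primary analysis as a linear regression of change in log10 sCD14 on arm and continuous baseline log10 sCD14. State that log10 is used for sCD14 whatever the observed distribution, and whether the two draws are averaged before or after taking logs. Keep the arm-only model as a named sensitivity analysis.

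The cost is one degree of freedom and a few sentences. No participants, visits or samples are added, and the adjusted model is already planned. Protocol 9.5 and SAP 2.11.2 have the stored specimens assayed in batches after follow-up ends, so the scale and model can be fixed before any sCD14 result exists.

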#### 9.6.2 Secondary Analyses

Similar to the initial primary analysis regression model, changes in other outcome measures will be compared between the Visbiome Extra Strength and placebo arms by linear regression. For these models each participant will have a single outcome measure of change from baseline to week 26. The only predictor variable will be study arm.

The weeks 26 and 38 levels of the primary, secondary, and exploratory outcome measures will be compared with baseline levels through linear regression.

Spearman correlations will be used to evaluate correlations between changes in select outcome measures. In addition, longitudinal changes in these measures will be examined using graphical approaches, descriptive statistics, and possibly repeated measures modeling.

Safety will be evaluated by summarizing the nature and rate of AEs within each study arm for all participants initiating study product. Comparisons of overall and AE-specific grades between study arms will be evaluated with an exact test for ordered categorical data (Wilcoxon rank-sum test of the maximum grade for each participant). Study product tolerability will be evaluated by summarizing study product modifications and discontinuations by study arm.

#### 10.0 PHARMACOLOGY PLAN

Not applicable

# 11.0 DATA COLLECTION AND MONITORING AND ADVERSE EVENT REPORTING

#### 11.1 Records to Be Kept

Case report forms (CRFs) will be provided for each participant. Participants must not be identified by name on any CRFs. Participants will be identified by the patient identification number (PID) and study identification number (SID) provided by the ACTG DMC upon randomization/registration.

#### 11.2 Role of Data Management

- 11.2.1 Instructions concerning the recording of study data on CRFs will be provided by the ACTG DMC. Each CRS is responsible for keying the data in a timely fashion.
- 11.2.2 It is the responsibility of the ACTG DMC to assure the quality of computerized data for each ACTG study. This role extends from protocol development to generation of the final study databases.

#### 11.3 Clinical Site Monitoring and Record Availability

- 11.3.1 Site monitors under contract to the NIAID will visit participating clinical research sites to review the individual participant records, including consent forms, CRFs, supporting data, laboratory specimen records, and medical records (physicians' progress notes, nurses' notes, individuals' hospital charts), to ensure protection of study participants, compliance with the protocol, and accuracy and completeness of records. The monitors also will inspect sites' regulatory files to ensure that regulatory requirements are being followed and sites' pharmacies to review product storage and management.
- 11.3.2 The site investigator will make study documents (eg, consent forms, drug distribution forms, CRFs) and pertinent hospital or clinic records readily available for inspection by the local IRB, the site monitors, the NIAID, the OHRP, and the industry supporter or designee for confirmation of the study data.
- 11.4 Expedited Adverse Event Reporting to DAIDS
  - 11.4.1 Adverse Event Reporting to DAIDS

Requirements, definitions and methods for expedited reporting of Adverse Events (AEs) are outlined in Version 2.0 of the DAIDS EAE Manual, which is available on the RSC website at http://rsc.tech-res.com/safetyandpharmacovigilance/.

The DAIDS Adverse Events Reporting System (DAERS), an internet-based reporting system, must be used for expedited AE reporting to DAIDS. In the event of system outages or technical difficulties, expedited AEs may be submitted via the DAIDS EAE Form. For questions about DAERS, please contact DAIDS-ES at [contact]. Site queries may also be sent from within the DAERS application itself.

Sites where DAERS has not been implemented will submit expedited AEs by documenting the information on the current DAIDS EAE Form. This form is available on the RSC website: http://rsc.tech-res.com/safetyandpharmacovigilance/. For questions about EAE reporting, please contact the RSC ([contact]).

#### 11.4.2 Reporting Requirements for this Study

- The SUSAR Reporting Category, as defined in Version 2.0 of the DAIDS EAE Manual, will be used for this study.
- The study agents for which expedited reporting are required is: Visbiome Extra Strength and the placebo for Visbiome Extra Strength.
- Grade 2 and higher adverse events related to the flexible sigmoidoscopy and rectal biopsy procedures performed in A5352s.

